6.1.3. Dosing and Administration

Participants will receive a 600 mg BID loading dose of study drug for the first day, followed by 400 mg QD for 29 days. All study drug doses will be oral self-administrations. Study drug will be supplied as 200 mg tablets.

6.1.4. Rationale for Selection of Dose

Hydroxychloroquine is an aminoquinolone antimalarial agent that is also approved and used for the treatment of autoimmune diseases including rheumatoid arthritis and systemic lupus erythematosus.

Studies have demonstrated *in vitro* activity of chloroquine against SARS-CoV. [17, 18] Both chloroquine and HCQ have been reported to have *in vitro* antiviral activity against SARS-CoV-2. [11, 12] *In vitro* testing using Vero cells vary; Yao et al demonstrated an EC50 of 23.90 and 5.47 uL for chloroquine at 24 and 48 hours respectively, compared to 6.14 and 0.72 for HCQ. [12] Liu et al reported on four multiplicities of infection (MOIs) (0.01, 0.02, 0.2, and 0.8); the 50% maximal effective concentration (EC50) for chloroquine was (2.71, 3.81, 7.14, and 7.36 µM) and for HCQ was (4.51, 4.06, 17.31, and 12.96 µM). Hydroxychloroquine may exhibit higher activity to chloroquine in protecting Vero cells from infection ("prophylaxis"); when Vero cells were pre-treated with drug before SARS-CoV-2 challenge, EC50 for chloroquine was >100 and 18.01 uL at 24 and 48 hours, respectively, compared to 6.25 and 5.85 for HCQ. [12] In animals, both drugs share similar tissue distribution patterns, with high concentrations in the liver, spleen, kidney, and lung reaching levels of 200–700 times higher than those in the plasma. [19]

The optimal dose of HCQ for treatment or prophylaxis is unknown. Absorption after oral dosing is incomplete and variable (~70% [range: 25 to 100%]). [20] Metabolism is primarily hepatic with metabolites including bidesethylchloroquine, desethylhydroxychloroquine, and desethylchloroquine. [21] The drug has long half-life elimination of approximately 40 days. [20]

Standard dosing in other medical conditions include: systemic lupus erythematosus (200-400 mg daily given once or divided BID), malaria treatment (800 x1, followed by 400 mg at 6, 24 & 48 h after initial dose), Q fever (600 mg/day in 1 to 3 divided doses) and rheumatoid arthritis (200-400 mg daily in 1-2 divided doses). The recommended maximum dose of HCQ is 5 mg/kg Actual Body Weight daily.

The dose chosen for this study is 600 mg orally BID on day 1 as a loading dose followed by 400 mg QD for an additional 29 days. This dose was chosen for several reasons:

- current in vitro studies report a wide range of EC50 for SARS-CoV-2,
- variability of absorption and of tissue distribution into the lung,
- due to a lack of phase 1b data for this drug in SARS-CoV-2 infection, the optimal pharmacokinetic/pharmacodynamic target is unknown.

Yao et al made assumptions regarding the absorption and tissue distribution that were optimistic and recommended as an optimal treatment dose 400 mg BID on day 1 as a loading dose followed by 200 mg BID daily for the remainder of the treatment course. [12] There is concern that this dose will not meet the necessary pharmacokinetic/pharmacodynamic targets for efficacy, in which case a negative study would not be due to failure of the antiviral efficacy but of suboptimal dosing. Yao et al also noted that the drug exposure was the same for 200 mg BID or 400 mg QD daily dosing. We propose a higher loading dose of 600 mg BID on day 1 to ensure more rapid steady state tissue distribution and 400 mg QD (versus BID) dosing for ease of dosing and adherence.

6.2. Placebo

6.2.1. Formulation, Appearance, Packaging, and Labeling

Placebo will be provided in a similar appearance as the study drug and be packaged and labeled in a masked manner in compliance with regulatory requirements.

6.2.2. Drug Dispensing, Storage, and Stability

A quantity of study drug sufficient for 30-days will be provided to the participant at enrollment. Placebo should be stored at room temperature (15°C - 30°C).

6.2.3. Dosing and Administration

All placebo doses will be oral self-administrations. Placebo tablets will be provided in a dose that mimics the pill count of the study drug (HCQ).

6.2.4. Rationale for Selection of Dose

N/A

6.3. Study Drug Accountability

Use of study drug will be tracked via the participant portal, call center, or final in-person study visit. Adherence to study drug as provided will be assumed unless reported otherwise.

Participants will dispose of any unused study drug as they would normally when stopping a medication.

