4.1. Overall Design

Potential participations will be pre-screened from the HERO Registry. Potentially eligible participants who indicate interest in trial participation in the HERO Registry and work at one of the 40 U.S. sites participating in this trial will be approached for participation in the HERO-HCQ trial. Please refer to Section 5.3 for more details about the recruitment and informed consent process. Approximately 2,000 HCWs from 40 U.S. sites will be enrolled in this trial and followed for ~60 days.

Eligible participants will be randomly assigned (1:1), stratified by site, to either treatment group (HCQ) or placebo in a double-blind fashion. After enrollment, baseline assessments will include nasopharyngeal swab for COVID-19 and a blood sample to assess baseline serology for SARS-CoV-2. For convenience, follow-up will be performed weekly through a direct to participant portal. A call center will provide support for any missed visits. Follow-up includes screening for COVID-19 clinical signs and/or symptoms, other respiratory infections, non-infectious clinical events, adverse events, and QoL assessments. For more details regarding follow-up procedures, please refer to Section 8.1.2.

A visit at approximately 30 days after randomization will be done on site to assess any subsequent clinical or safety events and adherence to study drug. A nasopharyngeal swab for COVID-19 and a blood sample will be obtained to assess for seroconversion for COVID-19 or other related tests.

An end of study visit will be conducted at approximately 60 days via the direct to participant portal or call center to assess for any subsequent clinical or safety events.

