10.6.6. Adherence and Retention Analysis

Treatment dropouts and consent withdrawals will be tracked by verifiable means at each follow-up assessment. Participants will be asked about their use of study drug during telephone follow-up. Those reporting discontinuation or switching will be asked about the reasons for discontinuation/switching.

Because study participants are HCWs, it is expected that this study will have excellent retention. Measures of study retention to inform follow-up time will be based on a number of measures, weekly web-based check-ins for symptoms and exposure history or in-person visit.

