11.5. Site Management and Quality Assurance

The study team will work in tandem to ensure that the data collected in this study are as complete and correct as possible. We will implement a four-step, multi-functional approach to quality control:

- Training: Prior to the start of enrollment, the clinician investigators and study coordinators at each site will be trained with the clinical protocol and data collection procedures, including how to use the Electronic Data Capture (EDC) system. Follow-up training and training for new study personnel will be conducted as needed.
- Monitoring: The CCC, along with the DCC, will ensure that data collection is handled properly, will provide in-service training, and will address questions from site investigators and coordinators. Review of data quality and completeness will occur on a regular and ongoing basis. Any issues will be addressed. There will be no on-site monitoring or source document verification.
- Managing data: After the data have been transferred for statistical summarization, data description, and data analysis, further crosschecking of the data will be performed with discrepant observations being flagged and appropriately resolved through a data query system.
- Reviewing data: Events of interest will be reviewed to ensure an appropriate standardized classification of the component events comprising the primary composite endpoint.

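### Section 6.3 counts participants who give no report as adherent, which biases recorded adherence upward and leaves a null result with high recorded adherence open to undetected non-use

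*Protocol*

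**What the plan says.** Section 6.3 names the sources of information: "Use of study drug will be tracked via the participant portal, call center, or final in-person study visit". It then sets the default, "Adherence to study drug as provided will be assumed unless reported otherwise", and deals with leftover tablets: "Participants will dispose of any unused study drug as they would normally when stopping a medication".

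Section 10.6.6 reads differently: "Treatment dropouts and consent withdrawals will be tracked by verifiable means at each follow-up assessment". It adds "Participants will be asked about their use of study drug during telephone follow-up", with reasons sought from those who stop or switch. Section 4.1 lists adherence among the things assessed at the Day 30 onsite visit. Section 11.6 expects the portal and call center to ask regularly about treatment taken. The introduction to Section 8 makes sites report permanent cessation of study drug.

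The visit lists in Sections 8.1.1 to 8.1.3 name no adherence item, and Table 1 shows study drug use only as a continuous line. Section 11.5 states: "There will be no on-site monitoring or source document verification". Section 10.7 includes adherence among the items that the DSMB monitors and that the DCC reports before each meeting.

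**The concern.** A default that turns an absent report into a favourable one does not average out: every silent non-user is scored as a user, and nothing offsets this. The protocol foresees silence, since it provides call-center support for missed visits (Section 4.1) and a procedure for loss to follow-up (Section 7.3).

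Other records would not necessarily expose quiet stopping. Section 2.3.1 lists nausea, diarrhea and allergic rash as risks of HCQ. Section 9.1.1 collects non-serious events only if they are Events of Special Interest, and the list in Section 9.1.4 contains neither gastrointestinal symptoms nor ordinary rash. The gap could therefore differ between arms, although the documents do not show that it would.

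At stake are the adherence rate shown to the DSMB and later published, and the reading of a null result. If recorded adherence is high partly because silence was scored as use, it cannot support the statement that the drug was taken and did not work.

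**Working it through.** **The default rule.** The protocol states no adherence figure to reproduce, so the bias is derived from the rule itself. Let

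- s = share of participants giving no report on use;
- u = share of those who are in fact non-users;
- r = non-use rate among those who do report, taken as truthfully reported.

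Recorded adherence under Section 6.3 = 1 − (1 − s)r.
True adherence = 1 − [(1 − s)r + su].
Difference = su, which is never negative and does not depend on r.

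If silence is coded as missing, the bounds are 1 − (1 − s)r (missing as adherent) and (1 − s)(1 − r) (missing as non-adherent). Their width is s.

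The documents give none of s, u or r. With r = 10% assumed throughout:

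| s | u | Recorded | True | Excess (su) | Lower bound |
|---|---|---|---|---|---|
| 5% | 20% | 90.5% | 89.5% | 1 point | 85.5% |
| 10% | 50% | 91.0% | 86.0% | 5 points | 81.0% |
| 20% | 50% | 92.0% | 82.0% | 10 points | 72.0% |
| 30% | 80% | 93.0% | 69.0% | 24 points | 63.0% |

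The recorded rate equals the upper bound in every row. With r fixed, it rises from 90.5% to 93.0% as silence rises from 5% to 30%: the less the trial hears, the better adherence looks.

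**Sections 6.3 and 10.6.6 side by side.** A participant who stops permanently and says nothing is a treatment dropout under Section 10.6.6, to be tracked verifiably. Under Section 6.3 the same participant is adherent. The means described elsewhere all depend on participant report, directly or through the site, so it is unclear what makes the tracking verifiable.

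**What the rule does not touch.** Section 10.2 gives 80% power with about 2,000 participants for 5% against 2.5%, and for 6.5% against 10%. The two-proportion formula with continuity correction (two-sided 0.05, 1:1) gives 984 per arm (1,968 in total) and 1,026 per arm (2,052), so the plan's figure reproduces. The inputs are the two risks, the error rates and the sample size. How adherence is recorded does not enter.

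**The case against.** The best reply is that silence is not the main data source. Use is asked about by telephone, through the portal and at the Day 30 onsite visit, reasons for stopping are sought, and sites must report permanent cessation. Section 6.5 requires discussion with the CCC before any dose modification. Section 10.6.6 expects excellent retention. If s is small the bias is small. That stands as an argument about size, but it does not remove the default for those who give no answer.

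It is also fair that Section 6.3 does not name non-responders or participants lost to follow-up, and that a statistical analysis plan could treat missing adherence data differently. However, the default is written as a rule on drug accountability. If only the assumed value is stored, no later analysis can separate it from a reported one.

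Several stronger readings are tempting and are not supported:

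- *That the rule costs power.* With benefit proportional to use, a 5% placebo risk and share a taking the drug, the HCQ risk is 0.05 × (1 − 0.5a). At a = 0.8 it is 3.0%, and continuity-corrected power at 1,000 per arm falls from 80.7% to 58.3%; at a = 0.7 it is 3.25% and 45.8%. True non-use causes that loss; the recording rule neither causes nor cures it.
- *That futility decisions rest on these figures.* Section 10.7 bases futility on predicted confidence intervals and conditional power for the endpoint. Adherence goes to the DSMB alongside.
- *That the protocol itself fears a null result from poor adherence.* The remark in Section 6.1.4, "in which case a negative study would not be due to failure of the antiviral efficacy but of suboptimal dosing", concerns whether a published dose would reach its pharmacological targets.
- *That counting is ruled out.* Section 6.3 says who disposes of unused drug. It describes no count, but does not forbid one.
- *That Sections 6.3 and 10.6.6 flatly contradict each other.* One mainly concerns ongoing dose-taking, the other discrete changes of status. They overlap for silent permanent stopping, where they fit poorly.
- *That no null result could be interpreted.* Reported discontinuation will be visible. The difficulty is confined to a null with high recorded adherence.

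**Conclusion.** The point holds as a defect in how adherence is recorded and reported. Applied as written, Section 6.3 adds su to true adherence, and that contribution is never negative. The size cannot be derived from the protocol: the range of 1 to 24 points rests wholly on assumed s and u, with truthful answers among reporters. If some reporters overstate their use, the total excess is larger.

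The primary comparison by assigned arm remains valid, and the protocol specifies no efficacy analysis that uses adherence. The consequence is limited to the adherence rates seen by the DSMB and by readers, and to how far high recorded adherence can rule out non-use as the explanation for a null result. It should be corrected, because the change is nearly free and the rule is explicit; it does not threaten the validity of the trial.

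**What to change.** 1. Delete the default sentence in Section 6.3.
2. Record the answer on study drug use at the existing contacts on Days 7, 14, 21 and 30, and name the item in the visit lists and Table 1.
3. Code non-response as missing and report its frequency by arm.
4. In Section 10.6.6, present adherence by arm with missing coded as adherent and as non-adherent, as upper and lower bounds.
5. Reconcile Sections 6.3 and 10.6.6: either say by what means dropouts are verified, or describe the data as participant-reported.

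The cost is about one portal item per contact, less where the question is already asked, and two extra lines in a table.

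Optionally, remaining tablets could be counted at the existing Day 30 onsite visit before disposal. The stated regimen amounts to 64 tablets of 200 mg (6 on day 1, then 29 × 2), so a count is feasible in a few minutes per visit. A deliberately low-burden, largely remote design could reasonably decline it. None of these changes alters dosing or clinical management.

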6.4. Concomitant Therapy

Select concomitant medications of interest that the participant is receiving at the time of enrollment or receives during the course of the study will be recorded along with dosing information. Select concomitant medications of interest include the following:

- Therapeutics that are being used in other COVID clinical trials
- Antibiotics
- Antifungals
- Immunosuppressants including steroids
- Tylenol
- Nonsteroidal anti-inflammatory drugs
- Angiotensin-converting-enzyme (ACE)/angiotensin II receptor blockers (ARB)/angiotensin receptor neprilysin inhibitor (ARNI)
- Statin
- HIV protease inhibitors including lopinavir, ritonavir, atazanavir, darunavir
- ribavirin

Prohibited medications include those at high risk for QT prolongation including:

- procainamide,
- disopyramide,
- mexiletine.
- flecainide.
- propafenone.
- amiodarone,
- sotalol.
- cimetidine
- dronedarone,
- dofetilide
- fluoroquinolones including ciprofloxacin, levofloxacin, moxifloxacin
- see MOP for full list of contraindicated medications

6.5. Dose Modification

This protocol allows some alteration from the currently outlined dosing schedule. The maximal daily dosing should not exceed what is specified in the protocol.

If moderate or severe adverse event (AE) occurs, that is, in the opinion of the investigator, reasonably attributable to study intervention, then dose may be altered by changing from QD to BID dosing, may be temporarily halted, or may be reduced, in consultation with the study CCC. Relevant reporting and discussion with the CCC study personnel, must take place prior to dose modification.

If the same SAE occurs consistently across participants, then dose or frequency of dosing may be reduced by trial leadership or per any DSMB recommendations.

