- Other potential toxicities including bone marrow suppression, arrhythmia, and hypoglycemia. These are not likely with a finite course of therapy. Furthermore, there is no evidence that G6PD deficiency is a problem with HCQ. While different class of antimalarial causes hemolysis with G6PD deficiency, there are no reports of hemolysis with HCQ.

Risk lowering measures: Study procedures to manage and minimize risks include careful selection of the participants and monitoring over time to check on participants' health. Additional guidance to manage any risks will be provided to the study teams, as needed. In addition, an independent DSMB will monitor safety of the participants throughout the study.

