7.1. Participant Withdrawal/Termination

Participants will be followed until participant closeout, withdrawal of consent, or death.

A participant may withdraw from the study at any time at his/her own request, or may be withdrawn at any time at the discretion of the investigator for safety, behavioral, compliance, or administrative reasons. This is expected to be uncommon.

Those who request withdrawal from the study will be asked to continue on study follow-up with limited participation through the Final Visit (Section 8.1.3). Limited participation may include a call at 30 days and 60 days to assess safety.

If the participant withdraws consent for disclosure of future information, the sponsor may retain and continue to use any data collected before such a withdrawal of consent.

If a participant withdraws from the study, he/she may request destruction of any samples taken and not tested, and the investigator must document this in the site study records.

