7.3. Lost to Follow-up

Participants will be asked for proxy contacts to assess vital status and/or other clinical events if a participant repeatedly fails to return for scheduled visits or does not participant in remote visits. A participant will be considered lost to follow-up if he or she repeatedly fails to return for scheduled visits or does not participate in remote visits and neither the participant nor his or her proxy can be contacted by the study site.

The following actions must be taken if a participant fails to return to the clinic or participate in remote visits as required by the study:

- The site must attempt to contact the participant and reschedule the missed visit as soon as possible and counsel the participant on the importance of maintaining the assigned visit schedule.
- The site or call center will contact the participant's proxy to assess vital status or other clinical or safety events.

- Before a participant is deemed lost to follow-up, the investigator or designee must make every effort to regain contact with the participant (where possible, three telephone calls and, if necessary, a certified letter to the participant's last known mailing address or local equivalent methods). These contact attempts should be documented in the participant's medical record. If safe, and appropriate, participants who fail to respond to study contact should be contacted at work by the study team since these participants are employees of the facility.
- Should the participant continue to be unreachable, he/she will be considered lost to follow-up.

8. Study Assessments and Procedures

The study site will perform the baseline visit, which includes randomization, if eligible. The site will confirm suitability to receive study drug. Sites will be responsible for notifying the coordinating center for participant withdrawals, lost to follow-up, permanent cessation of study drug, study drug dose modifications, or change in vital status. Data is being collected directly from participant and supported by medical records, as needed.

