9.1.1. Collection Period for AE and SAE Information

Study participants (and their designated emergency proxies) will be instructed to report Events of Special Interest (EOSI) and SAEs through their access to the study's participant portal. Events of special interest and SAEs will also be elicited during each remote follow-up visit and during the Baseline and Day 30 onsite visits. Participants will have access to AE reporting via the electronic portal from the signing of the informed consent form (ICF) until the Final Visit (Day 60).

Medical occurrences that begin before the start of study intervention but after obtaining informed consent will not be considered an AE.

Non-serious AEs will not be collected unless the event meets the criteria of an EOSI.

Events of Special Interest will be collected from the start of study drug until Final Visit or until 30 days after the last dose if participant early terminates the study.

Serious adverse events will be collected from the start of study drug until Final Visit or until 30 days after the last dose if participant early terminates the study.

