12.3. Protocol Deviations

A protocol deviation is defined as non-compliance with the clinical study protocol, GCP, or MOP requirements. The non-compliance may be on the part of the participant, site investigator, or the site staff.

A major protocol deviation is a significant divergence from the protocol that may have significant effect on the subject's safety, rights, or welfare and/or on the integrity of the study data. Major protocol deviations must be sent to the study IRB and local IRB per their guidelines, recorded in source documents, and reported to the coordinating center. Major protocol deviations will be tracked.

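### Section 6.5 requires discussion with the CCC before study drug may be temporarily held for safety, and the protocol has no urgent exception

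*Protocol*

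**What the plan says.** Protocol Section 6.5 sets the trigger as follows: "If moderate or severe adverse event (AE) occurs, that is, in the opinion of the investigator, reasonably attributable to study intervention". Three responses are then open: moving from once-daily to twice-daily dosing, a temporary halt, or a reduction. For the last two the wording is "may be temporarily halted, or may be reduced, in consultation with the study CCC". The next sentence fixes the order of events: "Relevant reporting and discussion with the CCC study personnel, must take place prior to dose modification".

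Section 7.1 deals with leaving the study. A participant "may be withdrawn at any time at the discretion of the investigator for safety, behavioral, compliance, or administrative reasons". It does not mention contact with the CCC beforehand.

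The opening paragraph of Section 8 sets the reporting duty: "Sites will be responsible for notifying the coordinating center for participant withdrawals, lost to follow-up, permanent cessation of study drug, study drug dose modifications".

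Section 12.3 defines the consequence of not following the rules: "A protocol deviation is defined as non-compliance with the clinical study protocol, GCP, or MOP requirements".

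Section 2.3.1 adds a general promise: "Additional guidance to manage any risks will be provided to the study teams, as needed".

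**The concern.** Section 6.5 applies only once the investigator has judged that the drug is probably responsible for a moderate or severe event. At that point a short hold is an obvious protective step, and it can be reversed. Some events of special interest in Section 9.1.4, such as ventricular arrhythmia, prolonged QT interval, angioedema and seizure, can call for a decision before the next dose. A rule that puts a conversation with a coordinating center ahead of the hold, with no exception, sets the wrong order for urgent cases. It also leaves the site investigator, who is responsible for the participant, choosing between the literal text and prompt action. What is at stake is participant safety and clear instructions to sites. Sample size, power, type I error and the analysis are not involved.

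**Working it through.** No figure in the protocol bears on this point, so the check is a comparison of the text.

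1. **Does the precondition reach a temporary hold?** Section 6.5 is headed as dose modification. It lists the halt in the same sentence as the schedule change and the reduction, and the next sentence applies the prior-discussion duty to dose modification without distinguishing among them. The natural reading is that all three are covered, including the halt.

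2. **Is there an exception for urgent cases?** Section 6.5 has none. Its last paragraph concerns the same SAE recurring across participants and gives powers to trial leadership and the DSMB, not to the site. Sections 7.1, 8, 9.1.1 to 9.1.4, 11.2 and 12.3 contain none either. Section 10.4 does put participant safety first, but only for decisions to unblind.

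3. **How does this compare with withdrawal?** Section 7.1 gives the investigator discretion at any time, names safety as a ground, and sets no prior step with the CCC. Section 8 then has the site notify the coordinating center. So the protocol allows immediate withdrawal for safety but not, on its wording, an immediate temporary hold.

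4. **What follows for a site that holds first?** Under Section 12.3 any non-compliance with the protocol is a deviation, so a hold followed by a call meets the general definition. Only major deviations must be sent to the IRBs, reported to the coordinating center and tracked. Those are deviations that may significantly affect safety, rights, welfare or data integrity. Nothing in the text makes a protective hold with a prompt call a major one.

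5. **How often would the order matter?** Under Section 6.1.3 dosing is 600 mg twice on the first day and then 400 mg once daily for 29 days. After the first day there are usually up to about 24 hours before the next dose in which to reach the CCC. On the first day, the second 600 mg dose could fall due sooner. The protocol states neither how many such events are expected nor how fast the CCC responds, so no frequency can be calculated.

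**The case against.** The strongest reply is that nobody is left exposed. Study drug is self-administered by mouth, so a participant can simply not take the next tablet. Section 11.2 separates a wish to stop drug from a wish to leave follow-up, and Section 7.1 gives the investigator an immediate exit. This stands, and it is why the point is minor.

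A second reply is that the working detail may lie elsewhere. Section 2.3.1 promises guidance to study teams, and other sections refer to the Manual of Procedures, which is not shown. An urgent-hold procedure may exist there, and its absence cannot be asserted. But Section 6.5 does not refer to the manual, and guidance allowing an immediate hold would conflict with an unqualified requirement in the protocol.

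A third reply is that prior contact has a purpose. Section 6.3 assumes adherence unless told otherwise, so early CCC involvement helps to capture holds and keep them consistent. That is a fair reason for wanting the CCC informed. Prompt notification after a safety hold serves most of it.

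**Conclusion.** The point holds as a minor defect of wording in a safety rule. Section 6.5 makes prior CCC discussion mandatory for every dose modification, a temporary safety hold included, and no exception is written anywhere in the protocol. The practical effect is small and no statistical result changes. The conclusion rests on reading the halt as a dose modification, which the heading and the sentence structure support.

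Three stronger readings are tempting, and the protocol does not support them:

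- A reader might infer that the mildest step carries the strictest precondition. In fact all three alterations carry the same one, and splitting the daily dose is arguably milder than a halt.
- A reader might infer that permanent cessation is expressly free of prior discussion. Section 8 lists permanent cessation and dose modifications together under one notification duty, and the protocol has no separate procedure for permanent discontinuation. Only the contrast with withdrawal under Section 7.1 is directly stated.
- A reader might try to size the defect by the dosing days lost if a site stopped drug for good, or by the shorter safety collection for early terminators in Section 9.1.1 ("until Final Visit or until 30 days after the last dose if participant early terminates the study"). That requires an unreachable CCC and a site that then chooses a larger step over a hold, and the protocol gives grounds for neither. Section 7.1 also provides for follow-up to closeout, so the realistic loss could be nil.

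**What to change.** Amend Section 6.5 so that the investigator may hold study drug immediately for safety and must notify the CCC promptly, for example within 24 hours. Keep prior CCC discussion for dose reduction, for the change from once-daily to twice-daily dosing, and for restart after a hold. Any guidance to sites should say the same.

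The cost is one or two sentences and a memo to sites. No visits, tests or data fields are added, because Section 8 already has sites notify the coordinating center of dose modifications. The downside is that the CCC learns of some holds afterwards, and a few may be holds it would have advised against. Requiring discussion before restart limits that.
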